## I.1. Introduction and Overview of the Study

### I.1.1. Synopsis

#### Purpose:

- Aim 1: To determine if an Occlusal Support Device (OSD) can reduce the duration of the second stage of labor
- Aim 2: To determine if an OSD can reduce the incidence of labor complications including Caesarian Sections
- Aim 3: To determine if the use of an OSD can improve Apgar scores in newborns.

**Design:** This is a randomized, intervention trial. Pregnant women who consent to participate will be enrolled; half will be randomized to have fabrication of an Occlusal Support Device (OSD) to be used during the second stage of labor. The other half will have no alteration in their normal pre or perinatal care. Enrollment is expected to take 24 months and subjects will be followed until delivery.

**Sample Size:** 500 women; all at the UMP Women's Health Specialists Clinic.

#### Inclusion Criteria:

- Nulliparous women
- Uncomplicated pregnancy
- Singleton pregnancy

#### Exclusion Criteria:

- Unable to provide informed consent or comply with study protocol,
- High risk and/or complicated pregnancy,
- Have multiple fetuses as diagnosed by ultrasound,
- Have extensive decay or multiple broken/missing teeth that will interfere with the fabrication of an OSD

#### Study Procedures

##### *Subject Recruitment*

We plan to recruit all of our study subjects from the UMP Women's Health Specialists Clinic. During their routine office visit for their pregnancy the participating physician or their affiliated nurse will make those patients who meet the study inclusion criteria aware of this study and ask them if they would

be interesting in hearing more information about the clinical study. Those patients who express a willingness to listen to a description of the study, will have the purpose of and procedures involved explained to them. Each woman will be given an opportunity to ask questions and given time to consider whether they would like to participate. For those women who would like to participate, oral and written informed consent will be obtained. Consenting participants will then be randomly assigned to one of the two study arms.

*Study Data:*

Baseline data will include the following:

- Maternal age
- Race
- Parity
- Height
- Body weight
- BMI
- Weight gain during pregnancy
- Number of missing teeth
- Overall dental health
- Temporomandibular dysfunction: presence or absence
- Vitals

*Dental Visit:*

Women who consent to participate in the study and are randomized to the intervention arm of the study will be scheduled for a dental examination. Participants will be seen at the UMP Adult Dental Clinic or Clinics and Surgical Center dental clinic for a general dental exam. Subjects randomized to the interventional arm of the study will also have impressions for fabrication of an OSD. They will be scheduled for a return visit to have the OSD tried in and adjusted if necessary.

*Post Delivery Data:*

An obstetrical nurse will abstract additional pertinent maternal health and birth information from the subject's medical record during labor including:

Woman:

- Gestational age at delivery

- Estimated fetal weight
- Indications for induction
- Use of oxytocin in labor
- Obstetrical complications
- Obstetrical interventions with indications
- Time of Second Stage Labor
- Use of epidural
- Vitals

Neonate:

- Birth weight
- Apgar score
- Head circumference
- Admission to the NICU and indications

Additionally, all women in the interventional group will be given a satisfaction survey relative to their experience with the OSD:

- 1- Disliked or refused use
- 2- not helpful
- 3- fair
- 4- helpful
- 5- very helpful

### **Outcome measures**

#### Primary Obstetrical Outcomes

- Time of Second Stage of Labor

#### Secondary Obstetrical Outcomes

- Complications of Pregnancy (C-section)
- APGAR Score of Neonate

#### **I.1.2. Background and Rationale**

- Importance

Prolonged labor, especially during the second stage of active expulsive effort (the pushing phase), is associated with increased risk of maternal complications (e.g. tissue trauma, postpartum hemorrhage, intra-amniotic infection). Developing an effective method to assist and maximize maternal expulsion effort should be of

great value in reducing the number of complications, also including cesarean section or instrumental deliveries. Past studies published in the dental literature have shown that specially designed oral appliances that support the dental occlusion may increase the isometric strength of different muscle groups. Increased strength of the neck muscles could improve efficiency of the Valsalva (pushing) maneuver in increasing intra-uterine pressure, and thus decreasing the duration of phase II of labor. It has also been shown that specially designed oral appliances can have an effect on neuro-endocrinology especially the Paraventricular nucleus of the hypothalamus and CRH levels, reducing cortisol levels in athletic stress. CRH having a role in the female reproductive system could be positively affected by the anti-stress properties of certain oral appliances.

- Improvement in scientific knowledge and clinical practice

This project could lead to an increased ability to determine when intervention during pregnancy utilizing an occlusal support device might decrease the incidence of caesarian section and other complications that occur during the second phase of labor.

- Changes based on this project if specific aims are achieved

If results are successful, routine clinical obstetrical care could include the fabrication of an OSD, thus utilizing a minimally invasive technique to positively impact the outcomes of labor.

### **I.1.3. Study Design**

**I.1.3.1. Overview.** This randomized, controlled clinical trial is designed to determine if the use of an OSD during second stage of pregnancy can reduce the duration of that stage thereby decreasing the risk for complications and lead to improved neonate outcomes. Five hundred women, in their first, second or third trimester of pregnancy, will be randomized into interventional or control arms. After collection of baseline data, approximately half of the subjects will be randomly assigned to have fabrication of an OSD to be worn during the second stage of labor. Subjects randomized to the intervention arm of the study will have a comprehensive dental exam and OSD fabrication.

#### **I.1.3.2. Subject population, study intervention, outcome measures.**

***Subject Selection and Informed Consent.*** Potential subjects will be screened at the UMP Women's Health Specialists Clinic. Before a subject is enrolled in the trial, oral and written informed consent will be obtained in accordance with the policies of the respective institution's Human Subjects Protection Program.

Interpreters, for non-English speaking subjects, will be available to assist in the consent process.

**Inclusion Criteria.** To be eligible for randomization in this study, each subject must:

1. Nulliparous
2. Have an uncomplicated pregnancy
3. Have a singleton pregnancy
4. 18 or older

**Exclusion Criteria.** Subjects will be excluded from participation if they:

1. Are unable to provide informed consent or comply with study protocol,
2. Are high risk and/or have a complicated pregnancy,
3. Have multiple fetuses as diagnosed by ultrasound,
4. Have extensive decay or multiple broken/missing teeth that will interfere with the fabrication of an OSD

*Test group intervention: OSD during second stage of labor.* Subjects randomized to the test group will have an OSD fabricated during their first, second or third trimester of pregnancy for use during their second stage (pushing stage) of their labor.

*Control group: No deviation from routine pre and perinatal care.*

*Outcome measures.* The outcome measures are as follows.

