#### I.1.3.3. Procedures.

*Timeline and Enrollment Schedule.* Five hundred subjects will be recruited over 24 months.

*Subject Recruitment.* A flyer will be posted at the UMP Women's Health Specialty Clinic. Any interested women will be directed to the research assistant at the clinic and be given a structured oral presentation of the study and asked to sign a consent form before they are randomized. Women will also be approached by the participating physician asking if they are interested in participating.

*Obstetrical Data Collection.* At each site, the obstetrical nurse, research assistant or physician will abstract risk factors for premature birth and birth data from the subject's clinic record.

*Delivery of Essential Dental Care.* Subjects in the intervention arm of the study will be given the opportunity to obtain treatment at the UMP Adult Dental Clinic or at the patient's oral health care provider of choice for abscessed or carious teeth detected during the dental examination.

Subjects will be free to seek dental care outside of the study. Patients will be financially responsible for any care delivered other than an oral exam.

*Coordination of Visits.* Study dental visits will be scheduled to coincide as much as possible with the subject's routine monthly prenatal visits.

*Subject Payment.* At the conclusion of the study, subjects will be given a \$10 gift card for use at a discount store (e.g., Target, Walmart, K-Mart). The gift card can be used to purchase items but cannot be redeemed for cash.

*Data Transmission.* The Study Coordinator is responsible for maintaining a supply of case-report forms, and for data quality control. The Coordinator will keep a photocopy of all forms in a secure, locked file cabinet.

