#### I.1.3.4. Statistical considerations.

##### *Statistical Analyses.*

The sample size is based on Aim 1. A sample size of 247 per group will have 90% power to detect a mean difference of 12 minutes between groups using a two group t-test at the 0.05 level of significance and assuming a standard deviation of 41.

For aim 2, this sample size of 247 per group will have 86% power to detect differences of a 1.2% Caesarean section rate in the OSD group and a 6.4% Caesarean section rate in the control group using a chi-square test at the 0.05 level of significance. For aim 3, 247 per group will have 90% power to detect a

mean difference in Apgar scores of 0.29 standard deviations using a two group t-test at the 0.05 level of significance.

Given that some patients will not reach second stage labor (e.g. Cesarean section prior to second stage labor), we plan to enroll additional patients to ensure that 247 patients per group reach the second stage of labor.

The planned statistical analyses are designed to address each specific aim. Descriptive statistics will be calculated for demographics, patient characteristics, and outcomes. The distributions and skewness of the continuous outcomes will be evaluated.

**Aim 1:** To determine if an OSD can reduce the duration of the second stage of labor

Mean duration of second stage labor will be compared between the OSD and control groups using a two group t-test. We will also explore the effect of important covariates (e.g. epidural or oxytocin use) on duration of second stage labor and whether this effect differs by group using linear regression models. Since some women will likely undergo a caesarean section or operative vaginal delivery during second stage labor, time from onset of second stage labor until delivery will be compared between groups using a log-rank test. Women undergoing these procedures will be censored.

**Aim 2:** To determine if an OSD can reduce the incidence of labor complications including Caesarian Sections

Rates of labor complications (including Caesarian Sections) will be compared between the OSD and control groups using chi-square tests or Fisher's exact tests. Similar to aim 1, we will also explore the effect of important covariates (e.g. epidural or oxytocin use) on rates of labor complications and whether this effect differs by group using logistic regression models.

**Aim 3:** To determine if the use of an OSD can improve Apgar scores in newborns.

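### Women can be randomised late in the third trimester with no minimum lead time for the two dental visits, so some OSD-arm women can reach second stage without a device and dilute the Aim 1 effect

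*Combined protocol and SAP*

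**What the plan says.** All references are to the combined protocol and SAP.

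- **Who is randomised, and when.** I.1.3.1 (Overview): "Five hundred women, in their first, second or third trimester of pregnancy, will be randomized into interventional or control arms". I.1.3.2, on the test group: "Subjects randomized to the test group will have an OSD fabricated during their first, second or third trimester of pregnancy". The eligibility lists in the Synopsis and in I.1.3.2 contain no latest gestational age and no minimum time to the due date. Both have a general exclusion for women who cannot follow the protocol.
- **What the OSD arm must complete after assignment.** Under Dental Visit in the Synopsis, women are scheduled for a dental examination once they are randomised to the intervention, and impressions are taken. A second visit follows: "They will be scheduled for a return visit to have the OSD tried in and adjusted if necessary". No fabrication time and no interval between the visits is given.
- **How the visits are timed.** I.1.3.3 (Coordination of Visits): "Study dental visits will be scheduled to coincide as much as possible with the subject's routine monthly prenatal visits".
- **What the sample size assumes.** I.1.3.4: "A sample size of 247 per group will have 90% power to detect a mean difference of 12 minutes between groups". This rests on a t-test at level 0.05 with an SD of 41. The only allowance is extra enrolment to replace women who never reach second stage. No analysis population is named, and nothing says how an OSD-arm woman without a device is to be analysed.

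**The concern.** The device does not exist at randomisation. It has to be made, tried in and if necessary adjusted in the time left before labor, and the plan does not require that enough time be left. A woman close to term who is assigned to the OSD may go into labor between the impression visit and the try-in visit, or before either.

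Such a woman, if she reaches second stage, counts toward the 247 in her arm. The planned extra enrolment does not replace her, because it replaces only women who do not reach second stage. She can contribute no device effect, so an as-randomised comparison is pulled toward zero. The cause would be the enrolment rule rather than a failure of the device or a woman's choice not to wear it. Leaving her out of the analysis is no remedy: the control arm has no matching exclusion, so the comparison would no longer be protected by randomisation. The problem can be prevented cleanly only before randomisation.

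**Working it through.** **Inputs from I.1.3.4:** difference 12 minutes, SD 41 (taken as minutes), 247 per group, level 0.05, power 90%. Sidedness is not stated. Two-sided is used because it reproduces the plan's number, whereas one-sided gives 200 per group.

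**Input not in the documents:** f, the share of OSD-arm women reaching second stage who have no device. Assumed values are 5%, 10% and 20%.

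**Step 1. Reproduce the plan's figure.** By the normal approximation,

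n = 2 × 41² × (1.960 + 1.2816)² / 12² = 2 × 1681 × 10.507 / 144 = 245.3, so 246 per group.

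The exact t-test calculation gives 246.3, so 247 per group. Power at 247 is 90.1% by the t-test and 90.2% by the approximation. The stated 247 is correct on its own assumptions.

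**Step 2. Expected difference with non-receipt.** If women without a device have the control-arm mean and everyone is analysed as randomised, the expected difference is 12 × (1 − f).

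**Step 3. Power at 247 per group.** The standard error is 41 × √(2/247) = 3.689 minutes. Power ≈ Φ(12 × (1 − f) / 3.689 − 1.960).

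**Step 4. Sample size that would restore 90%.** n = 245.3 / (1 − f)², rounded up.

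| f (assumed) | Expected difference (min) | Difference / SE | Power | n per group for 90% |
|---|---|---|---|---|
| 0 | 12.0 | 3.253 | 90.2% | 246 |
| 5% | 11.4 | 3.090 | 87.1% | 272 |
| 10% | 10.8 | 2.927 | 83.3% | 303 |
| 20% | 9.6 | 2.602 | 74.0% | 384 |

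**Step 5. Sensitivity to method.** Mixing women with and without a device raises the OSD-arm variance to 41² + f(1 − f) × 12². At f = 10% this is 1681 + 12.96 = 1693.96, which hardly changes the SD. With this inflation and the exact t-test, power is 86.9%, 83.1% (0.8305) and 73.5% at 5%, 10% and 20%. The method therefore moves the result by at most about half a percentage point. The unknown value of f is what matters.

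**The case against.** The strongest reply is that the plan already leaves room to avoid the problem.

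- **The visit timing is flexible.** A reader might infer from Coordination of Visits that the two dental visits are a month apart, so that the device takes one to two months to be ready and nobody enrolled in the last weeks could receive one. The text does not support this. Visits coincide with monthly prenatal visits only as far as possible, and no turnaround is given, so both visits could be booked close together. This part of the objection stands. It shows that a fast route is permitted, not that one is required or that it would always be fast enough.
- **The general exclusion could be used.** Having the device made for use in labor is part of the protocol, so an investigator could screen out a woman with too little time as unable to follow it. That reading is available, but the exclusion names no gestational limit or lead time, and I.1.3.1 and I.1.3.2 expressly include the third trimester. It does not clearly screen out late presenters, and investigators could apply it differently.
- **The share affected is unknown.** A reader might estimate it by assuming that enrolment is spread evenly over pregnancy. The documents give no distribution of gestational age at enrolment, and a woman enrolled late is not necessarily a woman without a device. If few women enrol late, the loss is near or below the smallest value shown.
- **Enrolment in any trimester looks deliberate.** It is stated twice, and 500 women are to be recruited at one clinic in 24 months. A cut-off at a particular week could cost substantial recruitment, and nothing in the documents supports a specific week. This stands, and it favours a feasibility condition over a fixed week.

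**Conclusion.** The gap is real and modest. The text allows a woman to be randomised at any point in the third trimester, requires two dental visits after assignment, and sets no minimum lead time. Some OSD-arm women can therefore reach second stage without a device, and the Aim 1 sample size assumes the full 12 minutes.

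The size cannot be fixed from the documents. Even an assumed 5% without a device takes power from 90% to about 87%. At 10% it is about 83% and at 20% about 74%. These figures rest on three assumptions: analysis as randomised (no analysis set is named), no benefit without a device, and SD 41 with a two-sided test.

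A reader might conclude that dilution is certain, or that the 247 is miscalculated. Neither follows. Dilution depends on late enrolment actually occurring and on the analysis set. If women without a device were dropped, the problem would be selection bias instead. The 247 is arithmetically right for the assumptions stated.

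**What to change.** Add one condition to the eligibility criteria in I.1.3.2, and align the Synopsis lists and the any-trimester statement in I.1.3.1 with it: at screening, both dental visits and fabrication of the OSD can be scheduled to finish before the expected delivery date. The lead time should come from the dental clinic's own turnaround. The check must be made for every woman, in both arms, before her assignment is known, so that it cannot make the groups differ.

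In I.1.3.4, state that all randomised women stay in their assigned arm for the Aim 1 analysis, including any OSD-arm woman who goes into labor earlier than expected and has no device. The condition reduces such cases but cannot remove them.

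The cost is one eligibility line, one sentence in the analysis section, and a scheduling check at screening. Women who present too late to complete both visits are not randomised. They are the women least able to receive the intervention, so the loss to the trial should be small, though the documents give no figure for how many there would be.

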#### Primary Obstetrical Outcomes

- Time of Second Stage of Labor

#### Secondary Obstetrical Outcomes

- Complications of Delivery
- APGAR Score of Neonate

#### I.1.3.3. Procedures.

*Timeline and Enrollment Schedule.* Five hundred subjects will be recruited over 24 months.

*Subject Recruitment.* A flyer will be posted at the UMP Women's Health Specialty Clinic. Any interested women will be directed to the research assistant at the clinic and be given a structured oral presentation of the study and asked to sign a consent form before they are randomized. Women will also be approached by the participating physician asking if they are interested in participating.

*Obstetrical Data Collection.* At each site, the obstetrical nurse, research assistant or physician will abstract risk factors for premature birth and birth data from the subject's clinic record.

*Delivery of Essential Dental Care.* Subjects in the intervention arm of the study will be given the opportunity to obtain treatment at the UMP Adult Dental Clinic or at the patient's oral health care provider of choice for abscessed or carious teeth detected during the dental examination.

Subjects will be free to seek dental care outside of the study. Patients will be financially responsible for any care delivered other than an oral exam.

*Coordination of Visits.* Study dental visits will be scheduled to coincide as much as possible with the subject's routine monthly prenatal visits.

*Subject Payment.* At the conclusion of the study, subjects will be given a \$10 gift card for use at a discount store (e.g., Target, Walmart, K-Mart). The gift card can be used to purchase items but cannot be redeemed for cash.

*Data Transmission.* The Study Coordinator is responsible for maintaining a supply of case-report forms, and for data quality control. The Coordinator will keep a photocopy of all forms in a secure, locked file cabinet.

#### I.1.3.4. Statistical considerations.

##### *Statistical Analyses.*

The sample size is based on Aim 1. A sample size of 247 per group will have 90% power to detect a mean difference of 12 minutes between groups using a two group t-test at the 0.05 level of significance and assuming a standard deviation of 41.

For aim 2, this sample size of 247 per group will have 86% power to detect differences of a 1.2% Caesarean section rate in the OSD group and a 6.4% Caesarean section rate in the control group using a chi-square test at the 0.05 level of significance. For aim 3, 247 per group will have 90% power to detect a

mean difference in Apgar scores of 0.29 standard deviations using a two group t-test at the 0.05 level of significance.

Given that some patients will not reach second stage labor (e.g. Cesarean section prior to second stage labor), we plan to enroll additional patients to ensure that 247 patients per group reach the second stage of labor.

The planned statistical analyses are designed to address each specific aim. Descriptive statistics will be calculated for demographics, patient characteristics, and outcomes. The distributions and skewness of the continuous outcomes will be evaluated.

**Aim 1:** To determine if an OSD can reduce the duration of the second stage of labor

Mean duration of second stage labor will be compared between the OSD and control groups using a two group t-test. We will also explore the effect of important covariates (e.g. epidural or oxytocin use) on duration of second stage labor and whether this effect differs by group using linear regression models. Since some women will likely undergo a caesarean section or operative vaginal delivery during second stage labor, time from onset of second stage labor until delivery will be compared between groups using a log-rank test. Women undergoing these procedures will be censored.

**Aim 2:** To determine if an OSD can reduce the incidence of labor complications including Caesarian Sections

Rates of labor complications (including Caesarian Sections) will be compared between the OSD and control groups using chi-square tests or Fisher's exact tests. Similar to aim 1, we will also explore the effect of important covariates (e.g. epidural or oxytocin use) on rates of labor complications and whether this effect differs by group using logistic regression models.

**Aim 3:** To determine if the use of an OSD can improve Apgar scores in newborns.

Mean Apgar scores at 1 and 5 minutes will be compared between the OSD and control groups using two group t-tests.

*Reporting for Quality Management.* The principal investigator (PI) and Study Coordinator have responsibility for monitoring the trial. [name] will monitor overall study management, enrollment, and compliance with protocol. He will provide oversight to assure that quality data are collected, and that adverse events are reported in a timely manner.

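### Does the Aim 2 caesarean comparison need a stated event window and denominator before its 86% power can be relied on?

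*Combined protocol and SAP*

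**What the plan says.** The caesarean outcome is described in these places in the combined protocol and SAP:

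- Synopsis (I.1.1), Purpose, Aim 2: "To determine if an OSD can reduce the incidence of labor complications including Caesarian Sections". Section I.1.3.4 repeats the aim and compares these rates between the two groups by chi-square or Fisher's exact tests.
- Synopsis, Secondary Obstetrical Outcomes: "Complications of Pregnancy (C-section".
- I.1.3.2, under the same heading: "Complications of Delivery", with caesarean not named.
- I.1.2, Background and Rationale: "caesarian section and other complications that occur during the second phase of labor".

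The power statement in I.1.3.4 uses 247 per group for all three aims. For Aim 2 it says that "this sample size of 247 per group will have 86% power to detect differences of a 1.2% Caesarean section rate in the OSD group", against 6.4% in the control group. The next paragraph begins "Given that some patients will not reach second stage labor (e.g. Cesarean section prior to second stage labor" and says extra women will be enrolled so that 247 per group do reach that stage. Under Aim 1, the plan also expects some caesareans during second stage and censors them in the log-rank analysis. The device is "for use during their second stage (pushing stage) of their labor".

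**The concern.** The labels need not cover the same caesareans. One before labour fits a pregnancy or delivery complication but arguably not a labour complication. One in first stage is a labour complication but is outside second stage. The plan expects caesareans both before and during second stage and handles both for Aim 1, yet gives Aim 2 neither an event window nor an analysis population.

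Caesarean is the only complication with a power statement, and the device is not used until second stage, so earlier caesareans can only dilute the comparison. Two analysts could count different events and report different p-values, and the choice could be made after the data are seen. The 86% might also belong to a different comparison from the one tested.

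**Working it through.** **Inputs.** From I.1.3.4: n = 247 per group, p1 = 0.012 (OSD), p2 = 0.064 (control), level 0.05. I take the test as two-sided. From the synopsis and I.1.3.1: 500 women in two halves, so 250 per group. Not in the documents: q, the fraction of randomized women with a caesarean before second stage. I assume it equal in both arms and show a range.

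**Formula.** Power = Φ[(|p2 − p1| − 1.96·SE0)/SE1], where SE0 = √(2p̄(1 − p̄)/n), SE1 = √(p1(1 − p1)/n + p2(1 − p2)/n) and p̄ is the mean of the two rates.

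**1. The plan's figure.** p̄ = 0.038, SE0 = 0.01720, SE1 = 0.01704. Then (0.052 − 0.03371)/0.01704 = 1.07 and Φ(1.07) = 0.858. The 86% reproduces. Exact enumeration gives 89.8% for the uncorrected chi-square and 84.4% for Fisher.

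**2. Rates and test both mean all caesareans, 250 per group.** SE0 = 0.01710, SE1 = 0.01694, (0.052 − 0.03352)/0.01694 = 1.09, power 86.2%.

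**3. Second-stage rates, second-stage events counted over all randomized women.** N = 247/(1 − q) per group and rates (1 − q)p. Power is 85.8%, 85.7% and 85.7% at q = 1.2%, 5% and 10%.

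**4. Second-stage rates, but all caesareans tested.** Rates become q + (1 − q)p, with N = 247/(1 − q).

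| q (assumed) | N per group | OSD | Control | Power |
|---|---|---|---|---|
| 1.2% | 250 | 2.4% | 7.5% | 75.5% |
| 5% | 260 | 6.1% | 11.1% | 51.9% |
| 10% | 274 | 11.1% | 15.8% | 36.2% |

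For example, at q = 5%: SE0 = 0.02460, SE1 = 0.02451, (0.0494 − 0.04822)/0.02451 = 0.048, Φ = 0.519.

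**5. Illustrative p-values.** 247 × 0.012 ≈ 3 and 247 × 0.064 ≈ 16 events. Early caesareans add 260 − 247 = 13 per arm at q = 5%, or 274 − 247 = 27 at q = 10%.

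| Count | OSD | Control | Chi-square p | Fisher p |
|---|---|---|---|---|
| Second stage only | 3/247 | 16/247 | 0.0024 | 0.0037 |
| All, q = 5% | 16/260 | 29/260 | 0.043 | 0.060 |
| All, q = 10% | 30/274 | 43/274 | 0.10 | 0.13 |

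The arms differ by 13 caesareans in every row. Counting earlier ones adds noise but no bias, since they are taken as equal in both arms. The smallest expected count is (3 + 16)/2 = 9.5, so the usual rule points to chi-square throughout; the gap between the two tests is a separate matter from the event window.

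**6. The text side by side.** The aim and its analysis name caesareans without limiting them by stage, and compare the groups as randomized. The only denominator attached to 247 is women who reach second stage. In the rationale, the second-phase clause may qualify only the other complications, and the rationale does not define an outcome in any case. No section pairs second-stage rates with a test of all caesareans, which is what step 4 requires.

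**The case for a change.** The strongest case for a change is that the ambiguity is real and cheap to remove. The sentence about 247 women reaching second stage does not mention Aim 2, so reading it as the Aim 2 denominator is an inference. On that reading an earlier caesarean could not count, which sits badly with the broad synopsis label. The document gives no population for 1.2% and 6.4%, and step 5 shows that the same second-stage data can fall on either side of 0.05.

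A further point concerns the rates themselves. Suppose 6.4% covers all caesareans, a share s of them precedes second stage and is unaffected, and the rest falls in the ratio 1.2/6.4. The OSD rate is then 0.064s + 0.012(1 − s): 1.7%, 2.5% and 3.8% at s = 10%, 25% and 50%. Power at 247 per group is 75%, 56% and 26%.

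It stands that the labels differ and that the window is unstated. The inference that the 86% is in doubt does not stand. Step 4 needs a mismatch that the plan does not describe and a q that it does not give. The calculation with s replaces the planned OSD rate with a higher one, so it questions how optimistic the effect is, not how the outcome is defined. Reporting second-stage and all-caesarean counts together would be informative, but that is a preference.

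**Conclusion.** No change follows; this is a gap that analysts can fill sensibly. Read as written, Aim 2 compares labour complications, caesareans included, between the randomized groups, and that comparison is valid whatever the frequency of earlier caesareans. The Aim 1 log-rank analysis already requires knowing which caesareans fell in second stage, so either count can be produced without new data.

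The stated 86% is correct (85.8% at 247 per group). It holds at about that level when the rates and the test refer to the same caesareans: 86.2% for all caesareans at 250 per group, by the chi-square approximation the plan uses. The exact Fisher figure is a little lower, at 84.4%. The fall to 76%, 52% or 36% depends on mismatched definitions and on assumed early-caesarean fractions of 1.2%, 5% and 10%, equal in both arms. The documents do not settle which caesareans the two rates describe. Because the outcome is secondary and the sample size is set by Aim 1, neither enrolment nor the primary analysis is affected. The differing labels are an editorial matter.
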